### 3.3 Double-blind Extension Period

After completing the double-blind Core Period, all participants will enter the Extension Period for a minimum of 8 weeks and a maximum of 52 weeks.

Those participants who are not responders and not remitters at the end of the Core Period (see in this section, subsection Extension Follow-up duration for more details ), will be observed in an abbreviated Extension Period lasting 8 weeks only to obtain safety data and evaluate withdrawal and rebound effects of MIJ821. Because those participants did not respond to the treatment as defined in [Section 3.2](#) in the first instance, no retreatment will be provided in case of relapse. Those participants are allowed to adjust their SoC in their 8 weeks Extension Period, as necessary.

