#### Extension Period

If relapse criteria are met during the Extension Period, participants will be treated with the same blinded dose and regimen they received during the Core period, receiving three i.v. infusions of investigational treatment once every 2 weeks, for a total period of 6 weeks. Participants receiving placebo in the Core Period, will be randomized in a blinded manner at the time of the initial randomization to one of the active treatment arms to receive treatment for relapse in the Extension Period in case they meet the required criteria at the End of Core (see [Section 3.4](#) for more details).

Only one course of three i.v. infusions of investigational treatment once every 2 weeks will take place in the extension. No second course of retreatment will be allowed. In case of clinical worsening after retreatment for relapse, the patient would not receive further retreatment with

the study drug. Patient will be managed as per see [Section 3.3](#) subsection Follow up duration and [Section 3.4](#) subsection Relapse and Clinical Worsening.

Once the dose and dose regimen for Phase 3 have been selected following completion of the interim analysis, participants experiencing a relapse who have not yet started retreatment will receive the selected Phase 3 dose and regimen in a dose-blinded manner. Patients who have already started treatment for the relapse will continue on the originally assigned dose.

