### **6.3.2 Treatment assignment, randomization**

On Day 1, all eligible participants will be randomized via Interactive Response Technology (IRT) to one of the treatment arms. The qualified unblinded site personnel will contact the IRT after confirming that the participant fulfills all the inclusion/exclusion criteria. The IRT will assign a randomization number to the participant, which will be used to link the participant to a treatment arm. If the patient is allocated to the placebo treatment arm, IRT will not return any kit allocation. If the patient is allocated to the active treatment arm, IRT will assign a unique medication number.

The randomization numbers will be generated using the following procedure to ensure that treatment assignment is unbiased and concealed from participants and investigator staff. A participant randomization list will be produced by the IRT provider using a validated system that automates the random assignment of participant numbers to randomization numbers. These randomization numbers are linked to the different treatment arms, which in turn are linked to medication numbers. A separate medication list will be produced by or under the responsibility of Novartis Global Clinical Supply (GCS) using a validated system that automates the random assignment of medication numbers to packs containing the study treatment.

The randomization scheme will include the treatment assignment in both the Core period and Extension period. Participants who are randomized to one of the active MIJ821 arms in the Core Period, will be assigned to the same blinded dose and dosing regimen (i.e. 3 i.v. infusion of MIJ821 or 1 i.v. infusion of MIJ821 followed by 2 i.v. infusions of placebo) of MIJ821 in the Extension Period. Participants who are randomized to the placebo arm in Core Period, will be assigned to one of the MIJ821 treatment arms (equally to MIJ821 dose groups except for 0.0048 mg/kg every other week with only half proportion) in Extension Period.

The switch to optimal dose/dose regimen post interim analysis is defined in [Sections 3.3](#) and [Section 6.1.4](#).

The randomization scheme for participants will be reviewed and approved by a member of the Randomization Office.

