2.1.3 Analysis sets

The Randomized Set (RAS) consists of all randomized participants. The descriptions of population will be based on RAS.

The Full Analysis Set (FAS) comprises all randomized participants who received at least one dose of randomized study treatment. Participants will be analyzed according to the treatment they have been assigned to during the randomization procedure. The primary efficacy analysis for data in Core Period will utilize this analysis set.

The Safety Set (SAF) includes all participants who received at least one dose of study treatment. Participants will be analyzed according to the treatment received. In case participants take the wrong treatment (different with the assigned treatment), the first treatment received will be used in analysis. Safety analysis for data in Core Period will be based on SAF.

The Extension Set (ENS) is defined to include all subjects who joined Extension Period. Data collected during follow-up period will be analyzed based on ENS, and grouped by the assigned treatment in Core Period. In case participants take the wrong treatment during Core, the first actual treatment taken will be used for the analysis of safety data only. The analysis of data collected during extension period (before and after re-treatment period) will be based on ENS.

The Retreatment Set (RTS) is defined as a subset of SAF including participants who received at least one dose for the retreatment of relapse. Participants will be analyzed according to the treatment received for the first injection during the Retreatment Period. The efficacy and safety endpoints pertinent to Retreatment Period (see [Table 2-1](#)) will be analyzed based on RTS.

PK Analysis Set (PKS) includes all participants who provided at least one evaluable PK concentration. Determined PK concentrations may be excluded from the PKS (per the scientific judgement of the PK scientist, e.g. non-plausible concentrations). All subjects within the PK analysis set will be included in the PK data analysis. PK samples from subjects treated with MJJ821 will be measured and PK samples from placebo treated subjects will not be measured.

[REDACTED]

[REDACTED]

[REDACTED]

[REDACTED]

[REDACTED]

[REDACTED]

[REDACTED]

[illegible]

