2.6.1 Adverse events (AEs)

Treatment-Emergent Adverse Events (TEAEs) are defined as adverse events starting or worsening after the first dose of study medication and up to 2 weeks post the last dose. For relapsed participants who receive retreatment of MIJ821 in Extension Period, adverse events starting after 2 weeks post the last dose of Core Period up to the start of retreatment will not be counted as TEAEs. The missing onset date of AE will be imputed before identify the TEAE (see imputation rule in [Appendix 5.1.1](#))

The Medical Dictionary for Regulatory Activities (MedDRA) version 24.0 or later will be used to code Adverse Event (AE) to a SOC and a PT.

TEAEs will be analyzed separately for Core Period and Retreatment Period:

- The summary of TEAEs in Core Period (up to 2 weeks post the last dose) will be based on SAF
- The summary of TEAEs in Retreatment Period (up to 2 weeks post the last dose of retreatment) will be based on RTS

The number (and percentage) of participants with TEAEs will be summarized by following approach as defined in [Table 2-7](#), in terms of all TEAEs, Treatment-Emergent Serious Adverse Events (TESAEs), TEAEs leading to treatment discontinuation, treatment-related TEAEs or TESAEs and death:

- by treatment, primary system organ class and preferred term
- by treatment, primary system organ class, preferred term and maximum severity
- by treatment, Standardized MedDRA Query (SMQ) and preferred term
- by treatment, preferred term with most frequent (incidence rate $\geq 5\%$)

Table 2-7 AE Summaries of Subject Incidence

Category	by SOC and PT	by SOC, PT and maximum severity	by most frequent PT (≥ 5%)
All TEAEs	Y	Y	Y
TESAEs	Y		
AEs leading to treatment discontinuation	Y		
Treatment-related TEAEs	Y		
Treatment-related SAEs	Y		
Deaths	Y		

For all AEs tables presented by SOC and PT (and grade), the SOC's will be presented in alphabetical order and PTs will be ordered within the SOC by decreasing order of frequency. AE tables by preferred term only will be sorted in descending order of frequency.

A participant with multiple adverse events within a primary system organ class is only counted once towards the total of the primary system organ class.

All AEs, deaths, SAEs and AEs leading to permanent study drug discontinuation will be listed separately.

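### SAP 2.1.3 groups Extension follow-up after MIJ821 retreatment by the Core arm, and the readable plan has no by-arm table of off-treatment adverse events

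*SAP*

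**What the plan says.** SAP 2.1.3 defines ENS as everyone who enters the Extension and sets the grouping: "Data collected during follow-up period will be analyzed based on ENS, and grouped by the assigned treatment in Core Period". The same paragraph extends the set across retreatment: "The analysis of data collected during extension period (before and after re-treatment period) will be based on ENS". It makes one exception: "In case participants take the wrong treatment during Core, the first actual treatment taken will be used for the analysis of safety data only". That exception concerns errors in Core and does not address retreatment.

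The Retreatment Set (RTS) follows a different rule: "Participants will be analyzed according to the treatment received for the first injection during the Retreatment Period". SAP Table 2-1 ends the Retreatment Period at the last Retreatment visit.

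Protocol 6.3.2 says of retreatment: "Participants who are randomized to the placebo arm in Core Period, will be assigned to one of the MIJ821 treatment arms". Protocol 6.1.4 adds that once a Phase 3 dose has been chosen, "participants experiencing a relapse who have not yet started retreatment will receive the selected Phase 3 dose and regimen in a dose-blinded manner".

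On adverse events, SAP 2.6.1 closes the treatment-emergent window two weeks after the last dose. For participants who are later retreated it adds that "adverse events starting after 2 weeks post the last dose of Core Period up to the start of retreatment will not be counted as TEAEs". Protocol 3.3 gives the purpose of the 8-week abbreviated Extension for participants who are neither responders nor remitters: "only to obtain safety data and evaluate withdrawal and rebound effects of MIJ821".

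**The concern.** There are two related gaps in how Extension data are reported.

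The first is the label. A placebo participant who relapses and is retreated with MIJ821 appears under the drug received during the Retreatment Period, then goes back to being called placebo for the rest of follow-up. An active-arm participant who relapses after dose selection may likewise be shown under a dose other than the one last received. A reader of any by-arm Extension output could attribute a late discontinuation, or its reason, to the wrong exposure.

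The second is coverage. The protocol collects adverse events to End of Study and gives withdrawal and rebound as a reason for the short Extension. The population has suicidal ideation with intent, and suicidality is an adverse event of special interest (AESI). If off-treatment events are only listed, the arms cannot readily be compared on the question that follow-up was set up to address.

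**Working it through.** **1. Is there follow-up after retreatment to be mislabelled?** Protocol 3.3 and 6.1.4 give a 52-week maximum, a 6-week retreatment course and at least 8 weeks of follow-up after it. The latest relapse that allows retreatment is 52 − 6 − 8 = 38 weeks, which is the protocol's own figure. A retreated participant therefore has at least 8 planned weeks after the course. In the protocol's example (retreatment in Weeks 19 to 25), 52 − 25 = 27 weeks remain, with seven visits (Weeks 28, 32, 36, 40, 44, 48 and 52).

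**2. Which set and label apply to each segment?**
- Before retreatment: ENS, by Core arm. This is correct.
- First retreatment dose to last Retreatment visit: RTS, by treatment received. This is correct.
- After the last Retreatment visit: ENS, by Core arm. Here the label no longer matches exposure. Placebo participants have been spread over six active regimens in the ratio 1:2:2:2:2:2, or given the selected Phase 3 regimen if they start after the interim.

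No readable sentence censors, splits or relabels the third segment.

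**3. Which visible outputs use the third segment?**
- MADRS summaries and the mixed model (SAP 2.4.6) stop at the two-week follow-up, whose window closes on Day 64 (Table 2-2). A full retreatment course starting on Day 44 at the earliest ends on Day 44 + 42 = Day 86. Not affected.
- Relapse proportion and Kaplan-Meier time to first relapse (SAP 2.5.2) count an event that precedes retreatment. Not affected.
- Laboratory and vital-sign summaries run to the two-week follow-up, with Retreatment shown separately. Not affected.
- Monthly visits are left out of by-visit summaries unless otherwise specified (SAP 2.1.2).
- Extension completion and discontinuation with reasons is shown by randomized treatment on ENS (SAP 2.2.1). Affected.
- Listings by treatment arm (SAP 2.1) and any other ENS summary that runs past retreatment. Affected.

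**4. How many participants?** The documents give 30 planned for placebo but no placebo response or relapse rate, so the count cannot be derived. As an illustration only, assume 30% to 70% are responders or remitters and 10% to 50% of those are retreated:
- low: 30 × 0.30 × 0.10 = 0.9
- high: 30 × 0.70 × 0.50 = 10.5

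That is roughly 1 to 11 participants, or 3% to 35% of the arm. The width of the range shows how little is known.

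**5. Adverse-event coverage.** With the last Core dose on Day 29, the window closes at Day 29 + 14 = Day 43, the End of Core visit. The abbreviated Extension runs 8 weeks from there, to Day 43 + 56 = Day 99, so all of it lies outside the window. In retreatment, Day 29 + 14 = retreatment Day 43, the End of Retreatment visit, so later events fall outside again. SAP 2.6 analyses safety for Core (SAF) and Retreatment (RTS) unless otherwise stated. The treatment-emergent summaries (2.6.1) and AESI summaries (2.6.1.1) name only those two periods. For other times the readable text provides listings.

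**The case against.** The strongest reply is that no visible drug-placebo comparison rests on the mislabelled data. A reader might infer that the placebo reference is contaminated and that late safety or durability differences are diluted. The documents do not support that. Step 3 shows that the efficacy, relapse, laboratory and vital-sign analyses stop before post-retreatment follow-up or precede it, and no by-arm table of late adverse events exists to be diluted. Nor does the label distort the withdrawal and rebound group: non-responders are never retreated, so Core-arm grouping is clean there. This part of the reply stands.

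It can also be said that retreatment was pre-randomized on Day 1, so the Core arm identifies a randomized strategy, and that disposition by randomized arm is conventional. This stands only in part. The SAP does not describe the grouping as a strategy comparison, RTS already switches to treatment received, and the regimen given after the interim depends on calendar time.

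On adverse events, the protocol's safety endpoint is limited to Core and the SAP window follows protocol 12.5.2, so the SAP does not depart from the protocol. Suicidality analyses may also exist out of sight: the SAP's change history names a section on suicidality (2.10.2), and its numbering jumps from 2.6.4.2 to 2.6.4.6. It cannot be said that suicidality scales go unanalysed in follow-up. The AE section and Table 2-7 are readable, however, and they contain no off-treatment table.

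**Conclusion.** The point holds and should be corrected, but it is a reporting defect of limited reach. Read literally, SAP 2.1.3 labels follow-up after retreatment by the Core arm. That is wrong for every retreated placebo participant, and for active-arm participants switched after the interim to a regimen other than their own. The visible consequence is confined to Extension disposition, listings by arm and any further ENS summary past retreatment. No count of affected participants, and no bias in any estimate, can be derived from the documents.

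The second part does not depend on any assumed rate. For participants dosed on schedule, the off-treatment follow-up has AE listings but no by-arm AE table in the readable plan, although the protocol gives safety, withdrawal and rebound as its purpose.

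Both conclusions rest on the readable text. Redacted sections could hold further handling, in particular of suicidality scales.

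**What to change.** In SAP 2.1.3, end Core-arm ENS summaries at the first retreatment infusion. Report later follow-up by Core arm and retreatment received, with placebo-then-MIJ821 as its own group, and carry the same labels into Extension disposition and listings.

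In SAP 2.6.1, add one descriptive table by Core arm of AEs, SAEs and suicidality AESIs, from 15 days after the last Core dose to the first retreatment infusion or End of Study. Give person-time denominators, because planned follow-up is 8 weeks for some participants and up to 52 for others.

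The cost is SAP wording, one period flag and one extra table, with no change to conduct or data collection. Cells will be small once split by Core arm and retreatment, so these outputs should be descriptive, without testing.

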## 1.2 Purpose

The main purpose of the study is to support dose selection for future Phase 3 clinical trials by evaluating the efficacy and safety of four MIJ821 doses (0.0048, 0.016, 0.048 and 0.16 mg/kg) administered every other week by intravenous infusion on top of pharmacological antidepressant treatment, compared with placebo plus pharmacological antidepressant treatment, for the rapid reduction of the symptoms of MDD in participants who have suicidal ideation with intent. In addition, the study will explore the effect of single dose administration of MIJ821 0.16 and 0.048 mg/kg to treat MDD in participants who have suicidal ideation with intent.

The study will also have a 12-month Extension Period to explore durability of the effect of the study treatment and the effect of MIJ821 on relapses rate, as well as safety of repeated MIJ821 administration.

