## Study treatment

Participants who are classified as responders or remitters at the end of the Core Period (see [Section 3.2](#) for more details), will be eligible to one retreatment course in case of a relapse

in the Extension Period, and should be observed for up to 52 weeks or clinical worsening after retreatment, whichever comes first (see in this section, subsection Extension Follow up Duration, and [Section 3.4](#)).

In the event of relapse (see [Section 3.4](#) retreatment in case of relapse), participants will receive study treatment (called retreatment), as in the Core Period, in a blinded manner. All participants will be pre-randomized to relapse retreatment on Day 1 in the Core Period as described below:

- Participants who were receiving MIJ821 in the Core Period will be assigned to the same dose and regimen for the retreatment in case of relapse (if any in the Extension Period)
- Participants who were randomized to placebo in the Core Period will be assigned to one of the active treatment arms in the Extension Period (see [Section 6.3.2](#))

After the dose and dose regimen for Phase 3 have been selected after the interim analysis, participants who relapse will receive the selected Phase 3 dose and regimen in a dose-blinded manner for the retreatment in case of relapse. Patients who have already started retreatment for the relapse will continue on the originally assigned dose.

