- Proportion of relapsing participants meeting response criteria or remission criteria after the first infusion of MIJ821 retreatment in the Extension Period
 - After the retreatment, the proportion of participants meeting response or remission criteria again will be derived based on all relapsing participants who have achieved response or remission at the end of Core Period.

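### The Retreatment Set tables combine first MIJ821 exposure in former placebo participants with re-exposure, so as visibly specified they do not isolate repeat exposure

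*SAP*

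**What the plan says.** **Who is in the set and how it is grouped.** SAP 2.1.3 defines the Retreatment Set (RTS) as a "subset of SAF including participants who received at least one dose for the retreatment of relapse". Former placebo participants are not excluded. The grouping rule is "Participants will be analyzed according to the treatment received for the first injection during the Retreatment Period".

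**What former placebo participants receive.** Protocol 3.3 (Study treatment) says "Participants who were randomized to placebo in the Core Period will be assigned to one of the active treatment arms in the Extension Period". Protocol 6.3.2 repeats this and gives the split: "equally to MIJ821 dose groups except for 0.0048 mg/kg every other week with only half proportion".

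**What former MIJ821 participants receive.** Until a Phase 3 dose and regimen has been chosen at the interim analysis, they repeat their own Core dose and regimen. After that choice, "participants who relapse will receive the selected Phase 3 dose and regimen in a dose-blinded manner for the retreatment in case of relapse". Anyone already in retreatment stays on the dose first assigned (Protocol 3.3 and 6.1.4).

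**What uses the RTS.** Retreatment exposure (SAP 2.3.1), retreatment MADRS (2.4.6), response or remission after the first retreatment infusion (2.5.2), and the retreatment safety analyses, including TEAEs and AESIs (2.6). For the response endpoint, SAP 2.5.1 says "the proportion of participants meeting response or remission criteria again will be derived based on all relapsing participants" who were responders or remitters at the end of Core.

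**What the Extension is for.** Protocol 1.2 lists durability and relapse rate, "as well as safety of repeated MIJ821 administration". Protocol 4.1 also gives safety after repeated use as a reason for the Extension.

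The Extension Set is grouped by Core assignment, but SAP 2.1.3 applies it to extension data before and after retreatment, not to the retreatment itself.

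**The concern.** Under this rule one RTS column can hold three kinds of participant:

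- former placebo participants meeting MIJ821 for the first time;
- MIJ821 participants re-exposed to their Core regimen;
- after the interim selection, MIJ821 participants re-exposed at a different dose or regimen.

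They are not interchangeable. All had to complete the Day 29 infusion and be responders or remitters at Day 43, so the eligibility rule is the same for everyone. What differs is the treatment on which they met it. Previously exposed members have been filtered for tolerating and doing well on MIJ821; former placebo members did so on placebo plus standard of care.

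An AESI rate or a response rate from the combined column is neither a first-exposure rate nor a re-exposure rate. A change in tolerability or effect on re-exposure could be diluted, or a spurious one suggested, by the first-exposure members. A reader will naturally take a table labelled retreatment as evidence on repeat use.

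**Working it through.** **Inputs from the documents.** Planned arm sizes (Protocol 12.8.1, SAP 3): 15 at 0.0048 mg/kg and 30 in each of the other six arms, placebo included. Former placebo participants are spread over the six active arms with weights 1:2:2:2:2:2, which is 11 parts (Protocol 6.3.2).

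**The plan's own total.** 15 + 6 × 30 = 195, as stated. From the evaluable number, 177 × 1.10 = 194.7 and 177/0.90 = 196.7; both are close to 195. The documents give no planned number of retreated participants.

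**Share new to MIJ821 in each retreatment group.** Let r be the chance that a placebo participant is retreated, relative to a MIJ821 participant. This is not in the documents, so it is varied. With a former placebo participants pre-assigned to a regimen and n in its Core arm, the share is r·a/(r·a + n).

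- 30-participant arm: a = 30 × 2/11 = 5.45.
- 0.0048 mg/kg arm: a = 30 × 1/11 = 2.73, n = 15.

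The ratio a/n is the same in both cases, so the share is the same in every group:

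| r | Calculation (n = 30) | Share new to MIJ821 |
|---|---|---|
| 0.5 | 2.73/32.73 | 8.3% |
| 1 | 5.45/35.45 | 15.4% |
| 2 | 10.91/40.91 | 26.7% |

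**After the interim selection.** Suppose every retreatment came after the selection, the selected regimen had a 30-participant Core arm, and all arms reached retreatment equally often. The group would then be:

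- former placebo: 30/195 = 15.4%;
- same regimen as Core: 30/195 = 15.4%;
- other Core regimen: (165 − 30)/195 = 69.2%.

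Retreatments begun before the selection keep their assigned regimen, so at that regimen they add only same-regimen or former placebo members. Under these assumptions 69% is a ceiling, not an expected value. It also counts participants who had the same dose on the other schedule.

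**Effect on a reported rate (illustrative rates, not from the documents).** The shift is share × (first-exposure rate − re-exposure rate).

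- Event rate 10% on re-exposure and 25% on first exposure: 0.154 × 15 = 2.3 points, so 12.3% is reported. Over the range of shares, the shift is 1.2 to 4.0 points.
- Response 60% and 30%: 0.154 × (−30) = −4.6 points, so 55.4% is reported. Over the range, the shift is −2.5 to −8.0 points.

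**Counts.** If 10% to 30% of participants are retreated (assumption), that is 165 × 0.10 to 165 × 0.30 = about 17 to 50 re-exposures and 30 × 0.10 to 30 × 0.30 = 3 to 9 first exposures in the whole trial. A 30-participant arm would hold 3 to 9 re-exposed and 0.5 to 1.6 first-exposed participants. In a group of 10, one event is 10 percentage points.

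**The case against.** The tempting stronger reading is that the trial cannot report on its aim of repeated administration at all. The documents do not support that.

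- Under equal retreatment rates about 85% of each group is truly re-exposed.
- Four Core arms already receive three active infusions, so repeated dosing is observed there. What Core cannot show is re-exposure after relapse.
- Relapse proportions and time to relapse are reported by arm in the Extension Set, which is grouped by Core assignment. The relapse analyses are therefore untouched.
- Protocol 1.2 words the aim as exploratory, and the formal secondary safety objective covers Core only.

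Other points against also stand, wholly or in part. Grouping by treatment received follows the Safety Set convention. SAP 2.5.1 speaks of meeting the response or remission criteria again, which is literally true of former placebo participants; the SAP does not call it re-response to MIJ821. Prior exposure can be recovered from individual listings. The average shifts are small beside sampling error: at 55.4%, √(0.554 × 0.446/n) is about 16 points for n = 10 and 22 points for n = 5. A three-way split of every table over six regimens would make up to 18 cells, mostly empty.

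Finally, it cannot be confirmed that no split is planned. SAP 2.1 leaves treatment-arm handling to the table shells, and SAP 2.1.4 and text near the RTS definition are redacted.

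None of this answers the narrower point: no visible text separates first exposure from re-exposure in the retreatment summaries. That they are descriptive makes a separate column easy to add, since no test loses power.

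**Conclusion.** The point holds as a limited one. As visibly written, the RTS safety summaries and the retreatment response/remission endpoint mix first MIJ821 exposure with re-exposure, so those tables do not isolate what the Extension is meant to explore. The first-exposure share is about 15% under equal retreatment rates and 8% to 27% for r between 0.5 and 2; r is an assumption. Mixing of Core regimens could reach about 69% of the selected-regimen group, but only if all retreatments followed the interim, arms were retreated equally often and the selected regimen had a 30-participant Core arm. The likely distortion of an average rate is a few percentage points on the illustrative figures, though single events will be visible in groups this small.

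The primary analysis is unaffected. This is a cheap improvement in presentation, subject to the unseen shells and redacted text.

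**What to change.** In SAP 2.1.3, 2.5.2 and 2.6:

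- Present the key RTS summaries (TEAEs, AESIs, vital signs, MADRS, response/remission) by retreatment dose, with separate columns for Core placebo (first exposure) and Core MIJ821 (re-exposure). Carry the MADRS layout through to 2.4.6.
- Flag same versus different Core dose or regimen in the listings, or in an additional column where counts allow.
- Base any statement about repeat administration on the previously exposed column only, and describe former placebo participants as first exposure.
- If the table shells already do this, say so in 2.1.3.

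The cost is extra columns derived from randomization data already held; no new data are needed. The drawback is small cells, in tables that are descriptive in any case.
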